APPENDIX 1 – SCHEDULE OF STUDY ASSESSMENTS

APPENDIX 2 – INVESTIGATIONAL SITE LIST

APPENDIX 3 – DEFINITIONS

PROTOCOL SUMMARY

| | |
|--|--|
| Study Title: | Prospective Randomized Trial Comparing the Safety and Performance of the Interscope EndoRotor® Mucosal Resection System with Continued Ablative Therapy in Subjects with Refractory Dysplastic Barrett's |
| Protocol No. | CLIN 0010 / D |
| Study Design: | A prospective, multi-center, randomized trial to compare the safety and performance of the Interscope EndoRotor® Mucosal Resection System in subjects with refractory dysplastic Barrett's Esophagus |
| Patient Population: | Subjects with refractory Barrett's metaplasia after 3 failed radiofrequency ablations (RFA) |
| Primary Objective: | To evaluate the EndoRotor®'s ability to completely remove areas of Barrett's metaplasia considered refractory after 3 failed radiofrequency ablations (RFA). |
| Secondary Objectives: | 
1. To compare the EndoRotor® to standard of care ablative therapies by determining the percent reduction of activated fibroblasts in the region of resection and ablation, respectively.2. Assessment of post procedure pain (chest pain discomfort events requiring narcotic analgesic). |
| Primary Endpoints: | Primary Effectiveness Endpoint: Complete removal of areas of Barrett's metaplasia after no more than two treatments. Primary Safety Endpoint: Assessment of Adverse Events (incidence, relationship to device and severity) compared to the control arm and the medical literature. |
| Secondary Endpoint: | Percent reduction of the area with Barrett's esophagus that was resected or ablated during the initial treatment session through the final follow-up visits. |
| EndoRotor® Arm | Once final study eligibility has been confirmed (i.e. after 3 failed radiofrequency ablations (RFA), the patient will receive the EndoRotor® device. |
| Continued Ablative Therapy Arm: | The EndoRotor® will be compared to continued standard of care ablative therapies with currently available Radio Frequency Ablation (RFA) treatments and/or cryotherapy ablation with cleared cryotherapy devices. |
| Study Duration: | Subjects will be followed with biopsies of the resected areas at the time of surveillance endoscopies every 3 months until they have 2 consecutive negative endoscopies and biopsies (6 months) |
| Clinical Sites: | A minimum of 3 and up to 5 sites in the United States will enroll subjects. |
| Enrollment: | The sites will enroll a total of 120 subjects meeting all inclusion and exclusion criteria to reach a total of 110 evaluable subjects, allowing for 10 subjects lost to follow-up. It is anticipated that there will be a total of 55 evaluable subjects in each arm. |

| | |
|----------------------------|--|
| Inclusion Criteria: | 
1. Subjects who are ≥ 30 and < 79 years of age; inclusive of males and females.2. Subjects with a history of confirmed Barrett's esophagus with dysplasia (low-grade or high-grade) refractory to radiofrequency ablation 3 times.3. Residual Barrett's length is ≥ 1 cm and ≤ 6 cm.4. Histologic persistence of intestinal metaplasia (any non-squamous epithelial lesion) following treatment and failed eradication.5. Following 3 failed RFA procedures with no confirmed evidence of EAC and having confirmed no endoscopic and histologic evidence of EAC at the time of therapy.6. Subject capable of giving informed consent.7. Subject has a reasonable expectation for prolonged survival (greater than 5 years).8. Subject can tolerate repeated endoscopic procedures.9. Absence of strictures that preclude the passage of the endoscope10. Subjects with the ability to understand the requirements of the study, who have provided written informed consent, and who are willing and able to return for the required follow-up assessments through 6 months or 9 months, as indicated. |
|----------------------------|--|

| | |
|----------------------------|--|
| Exclusion Criteria: | 
1. Subject unable to give informed consent.2. Subject is unwilling to return for repeated endoscopies.3. Subject having 3 failed RFA procedures and confirmed endoscopic and histologic evidence of EAC at time of therapy.4. Residual Barrett's longer than 6 cm.5. Subjects with nodular Barrett's Esophagus.6. Subjects who are on aspirin or anticoagulant therapy who cannot stop it and have had bleeding problems during previous endoscopic treatments.7. Esophageal varices.8. Active esophagitis.9. Esophageal stricture preventing passage of endoscope or catheter.10. Any previous esophageal surgery, except fundoplication without complications.11. Medically uncorrectable hypotension or hypertension.12. Any condition that in the opinion of the investigator would create an unsafe clinical situation that would not allow the patient to safely undergo an endoscopic procedure (lack of medical clearance).13. Pregnant or lactating women or women of childbearing potential who do not employ a reliable method of contraception as judged by the Investigator, and/or are not willing to use reliable contraception for the duration of study participation.14. Patient has known severe psychiatric disorder, substance abuse, or other reason for being unable to follow trial follow-up instructions.15. Patient has a known significant concomitant illness with a life expectancy of <1 year.16. Patient is known to be currently enrolled in another investigational trial that could interfere with the endpoint analyses of this trial. |
|----------------------------|--|

| | |
|----------------------------|---|
| Primary Analysis: | Per protocol (subjects enrolled in the study and who met all I/E criteria and are treated with the device). |
| Expected Timelines: | 
Enrollment: September 2017 – September 2018
 
Last 6-month Follow-up: February 2019
 
Last 9-month Follow-up: May 2019
 
Total Timeline: ~ 21 - 24 months
 
Twelve (12) months to obtain a total of 110 subjects. Subjects who are negative on their surveillance will complete the study in a minimum of 6 months, while those who are positive and require repeat treatment will take 9 months. Those who fail could exit the study between 6 and 9 months after first treatment. The study should be completed between 21 and 24 months after the first subject is treated.
 |
| Study Device: | Interscope EndoRotor® Mucosal Resection System |

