An alternative technique that has been used is cryotherapy, a technique that delivers extreme cold temperature through a direct spray or via a radial balloon, but this is still a surface ablative therapy. Ablative therapies damage the surface cells creating significant artefact and do not provide histologic specimens potentially hampering decision making and delaying the diagnosis of advanced lesions until they become large enough to be grossly identified. There are limited solutions for refractory BE patients, thus making a clinical rationale to compare the safety and effectiveness of continued ablative therapy to the EndoRotor in a randomized study to salvage RFA failures. In a review of the experience at the Mayo Clinic, Rochester, Minnesota, 46 (18%) patients out of a consecutive cohort of 246 patients treated with radiofrequency ablation of the entire segment still had intestinal metaplasia after three therapies and were classified as refractory. Of these 46 patients, 37 (80%) eventually reached complete endoscopic ablation after a total median of 24 months of therapy (range 14-68 months). In this group, the type of therapy, including cryotherapy, additional radiofrequency ablation, or endoscopic mucosal resection resulted in similar rates of complete response ($p<0.28$). In addition, a recent study was reported by Canto, MI, et. al. on carbon dioxide cryotherapy in a mixed group of primary therapy and rescue therapy for refractory disease. The authors found a complete response of intestinal metaplasia of only 55% in a retrospective cohort of 64 patients at 12 months of initiating cryotherapy.⁽⁹⁾

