4.12 Inclusion Criteria

Candidates for this study must meet **ALL** of the following Inclusion criteria:

1. Subjects who are ≥ 30 and < 79 years of age; inclusive of males and females.
2. Subjects with a history of confirmed Barrett's esophagus with dysplasia (low-grade or high-grade) refractory to radiofrequency ablation 3 times.
3. Residual Barrett's length is ≥ 1 cm and ≤ 6 cm.
4. Histologic persistence of intestinal metaplasia (any non-squamous epithelial lesion) following treatment and failed eradication.
5. Following 3 failed RFA procedures with no confirmed evidence of EAC and having confirmed no endoscopic and histologic evidence of EAC at the time of therapy.
6. Subject capable of giving informed consent.
7. Subject has a reasonable expectation for prolonged survival (greater than 5 years).
8. Subject can tolerate repeated endoscopic procedures.
9. Absence of strictures that preclude the passage of the endoscope.
10. Subjects with the ability to understand the requirements of the study, who have provided written informed consent, and who are willing and able to return for the required follow-up assessments through 6 months or 9 months, as indicated.

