5.1.1 Baseline Evaluation, not greater than 3 months prior to the Index Procedure

The following baseline evaluations will be assessed and recorded on all subjects who provide written informed consent:

- Demographic information and medical history including risk factors
 - PT/PTT within 2 days of the procedure
 - Pregnancy test within 1 day of the procedure
 - Cryotherapy treatments
 - Assessment against Inclusion/Exclusion criteria
- Medical clearance within 1 week of the procedure
- Biopsy-proven RFA-recalcitrant Barrett's Esophagus with low- or high-grade dysplasia – within the past 3 months.

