5.5.3 Index Procedure

Once enrolled, each patient will be randomized into either the EndoRotor® mucosal resection arm or the control ablation arm. Randomization will occur within 2 weeks of the procedure. The investigators shall follow the technique described by the manufacturer's instructions as provided in the Instructions for Use.

Endoscopic treatment of the esophagus will be performed within 6 weeks of enrollment with outpatient video documentation of the residual Barrett's changes during upper endoscopy.

EndoRotor® Arm: At this point, the EndoRotor® will be set-up and used to resect the mucosa and submucosa to remove all gross visible disease. Lesions will be "lifted" using saline solution with dye such as Indigo carmine or Methylene Blue. Indelible ink (such as SPOT) will be injected into the region of the resection to identify the site after resection. If the lesion is circumferential, the endoscopist shall resect no greater than 270 degrees of the radial circumference of the esophagus to avoid stricture formation. The resection is taken down to the muscularis propria layer to ensure all of the mucosa and submucosa is removed in the area of persistence.

The EndoRotor® is set to either High Speed (1700 RPM) or low speed (1000 RPM) based on user preference and the vacuum is set to between 250 mmHg and 350 mmHg of negative pressure. The endoscopist will start the EndoRotor® motor using the left foot pedal, and will activate the cutting by depressing and holding the

right pedal down for as long as he wants to resect tissue. The procedure is repeated until the entire gross visible lesion has been removed down to the muscularis propria without entering the muscle layer. The specimen can be sent to Pathology by removing the filter in the specimen trap. A new filter is placed in the specimen trap allowing multiple lesions to be treated and analyzed histopathologically.

Continued Ablative Therapy Arm: The investigator shall exercise standard of care for continued ablative therapies namely RFA (HALO 90/60) and/or cleared cryotherapy devices. These will constitute two control devices. The investigator will choose the system in this arm. Operation of the each system will be done according to the manufacturer's instructions for use. The type of system used will be indicated on the case report forms.

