7.4 Statistical Analysis

The Primary effectiveness endpoint will be compared across treatment arms using a logistic regression, where the predictor variable is treatment arm with EndoRotor® coded 1 vs 0 for cryotherapy or ablative therapy (i.e., control). Covariates included in the model will be: subject's age, dysplasia (low-grade or high-grade), length of Barrett's lesion in cm, and duration of disease (months). The lower boundary of the predicted proportion

difference will be used to compare the two arms for the non-inferiority test and for the subsequent superiority test. In the event that missing data are present in the ITT analysis population, then multiple imputation will be performed with SAS procedures MIIMPUTE and MIANALYZE, as described in section 7.5.

The secondary endpoint, percentage reduction, will be compared using a Wilcoxon rank-sum test. In the event of missing data, The ITT analysis will be performed with data imputed by multiple imputation.

In the event of missing data, sensitivity analyses will be performed for the ITT analysis population using best case and worst case analyses as described below. Discrepant findings will be followed by tipping point analyses.

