7.5 Missing Data

1. If there are missing primary endpoint data, then ten imputations of missing binary primary endpoint will be produced using SAS PROC MI using the Markov chain Monte Carlo algorithm. The seed used to begin random number generation will be 20170623. The following variables will be used as predictors: site, subject's age, dysplasia (low-grade or high-grade), length of Barrett's lesion in cm, and duration of disease (months). Analysis with SAS PROC MIANALYZE will follow.
2. For the secondary endpoint, percentage reduction, ten imputations will be produced for the randomized cohort using SAS PROC MI. The seed used to begin random number generation will be 20170623. The Markov chain Monte Carlo method will be used to compute full imputations using the following variables: site, subject's age, dysplasia (low-grade or high-grade), length of Barrett's lesion in cm, and duration of disease (months). Analysis with SAS PROC MIANALYZE will follow.

The following secondary analyses will be performed to assess the sensitivity of the results to missing data for the primary effectiveness endpoint.

- The best-case scenario will assume success for all missing data treated with EndoRotor and failure for all missing data treated with control.
- The worst-case scenario will assume failure for all missing data treated with EndoRotor and success for all missing data treated with control.
- If the best and worst case analyses lead to different statistical conclusions, then a tipping point analysis will report the proportion of successes or failures for each arm at point the statistical conclusion would change.

A similar approach will be used for the continuous percentage secondary endpoint. Best case will assume 100% removal for EndoRotor® and 0% for control; worst case will assume 0% removal for EndoRotor® and 100% for control; If the results differ using the two imputation rules, then the imputed values will be incremented on 1% values until the point where the conclusion changes is identified.

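### Prior cryotherapy can be present at entry and appears to be a baseline item, but neither the primary model (7.4) nor the imputation models (7.5) use it: a cheap, low-priority improvement

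*Combined protocol and SAP*

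**What the plan says.** - **Entry.** The Protocol Summary and section 4.12 require disease "with dysplasia (low-grade or high-grade) refractory to radiofrequency ablation 3 times". A further criterion asks for "Histologic persistence of intestinal metaplasia (any non-squamous epithelial lesion) following treatment and failed eradication", which does not restrict the earlier treatment to RFA. None of the 16 exclusions in 4.13 mentions cryotherapy. The bar on other treatments in 4.10 is tied to randomization and does not read as a limit on treatment history.
- **Baseline record.** Section 5.1.1 lists "Cryotherapy treatments" among the evaluations for every consenting subject. The item is not defined, and neither 5.1.2 nor Appendix 1 repeats it.
- **Control treatment.** Section 5.5.3 allows RFA and/or cryotherapy: "The investigator will choose the system in this arm".
- **Primary model (7.4).** "Covariates included in the model will be: subject's age, dysplasia (low-grade or high-grade), length of Barrett's lesion in cm, and duration of disease (months").
- **Imputation (7.5).** For the primary endpoint: "The following variables will be used as predictors: site, subject's age, dysplasia (low-grade or high-grade), length of Barrett's lesion in cm", plus duration of disease. The secondary endpoint uses the same list.
- **Randomization (5.2).** 1:1 within site, with no stratification by treatment history.

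**The concern.** Some subjects could reach this trial after failing both RFA and cryotherapy. Their disease may be harder to clear, and in the control arm they may be given a type of treatment they have already had. If so, prior cryotherapy is a prognostic baseline variable, possibly more so under control than under EndoRotor. With 55 evaluable subjects per arm, chance could place noticeably more of them in one arm. Neither the design nor the model balances or adjusts for this directly. There is also a question of interpretation: a difference against continued ablation may mean something different in subjects who have never had cryotherapy, and no breakdown by this history is planned.

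**Working it through.** **Inputs from the documents.** Response 80% v 50%; n = 55 evaluable per arm; superiority power 91.6%; non-inferiority margin 10 points, with power over 95% (all 7.3); two-sided alpha 0.05 (7.1).

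**Assumed inputs**, because the documents give none: prevalence of prior cryotherapy q = 10% to 50%; response lower in these subjects by gE points under EndoRotor and gC points under control, with the overall rates held at 80% and 50%.

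**Step 1: reproduce the plan's figures.** Unadjusted variance V0 = (0.8×0.2 + 0.5×0.5)/55 = 0.41/55 = 0.00745, so SE = 0.0863.
- Superiority, pooled z: SE under the null = √(2×0.65×0.35/55) = 0.0910; (0.30 − 1.96×0.0910)/0.0863 = 1.41, power 92.1%, close to the stated 91.6%. Unpooled: 0.30/0.0863 − 1.96 = 1.51, power 93.5%.
- Non-inferiority: 0.40/0.0863 − 1.96 = 2.67, power 99.6%, in line with over 95%.

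The stated design reproduces.

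**Step 2: how large a chance imbalance is.** The SD of the between-arm difference in prevalence is √(2q(1−q)/55): 5.7 points at q = 10%, 7.6 at 20%, 8.7 at 30%, 9.5 at 50%. An imbalance of 10 points or more in either direction then occurs in about 19% of trials at q = 20% (10/7.6 = 1.31 SD) and 25% at q = 30% (10/8.7 = 1.14 SD).

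**Step 3: what an imbalance does.** The unadjusted difference moves by the imbalance times the mean gap g = (gE + gC)/2. For a 10-point imbalance:
- 20-point gap in control only: g = 10 points, shift 1 point
- 20-point gap in both arms: g = 20 points, shift 2 points
- 40 points in control and 20 in EndoRotor: g = 30 points, shift 3 points

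**Step 4: precision against an unadjusted analysis.** The adjusted variance is the average within-stratum variance plus q(1−q)(gE − gC)²/(2n). Subtracting it from V0, the fractional reduction simplifies to 2q(1−q)g²/0.41.

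| Gap | q = 10% | q = 30% | q = 50% |
|---|---|---|---|
| 30 points, control only (g = 15) | 1.0% | 2.3% | 2.7% |
| 20 points, both arms (g = 20) | 1.8% | 4.1% | 4.9% |
| 30 points, both arms (g = 30) | 4.0% | 9.2% | 11.0% |

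**Step 5: precision against the planned model.** The planned analysis is not unadjusted, so Step 4 overstates the gain. Trials were simulated with four covariates already in the model, one of them a duration term correlated 0 to 0.5 with prior cryotherapy. Adding the term reduced the variance of the difference by about 1–2% for a 20-point gap and 4–8% for a 40-point control gap. With no effect on response, it increased the variance by about 1%.

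**Step 6: power.** Applying these limits to the unadjusted variance as an approximation, an 8% cut gives SE = 0.0863×√0.92 = 0.0828 and power 95.2%. A 1% increase gives SE = 0.0863×√1.01 = 0.0868 and power 93.3%. The reference is 93.5%.

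**Step 7: validity without the term.** In simulation, the analysis that omits prior cryotherapy had a mean estimate of 0.299–0.301 for a true 0.30 and one-sided type I error of 2.3–2.6%.

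**The case against.** The strongest reply is that this is a covariate preference. Every randomized trial leaves some prognostic variable out, and the confidence interval already allows for chance imbalance. The plan pre-specifies four sensible covariates. Subjects with more failed treatments probably have longer disease duration, so part of any shift is already absorbed. Section 7.8.4 summarizes baseline characteristics, including medical history, by arm, so an imbalance might be seen. Section 5.1.1 does not say that the cryotherapy is prior or failed. All of this stands, and it is why the point is low priority. It does not explain why an apparent baseline item on treatment history, of the same kind as one control treatment, should go unused.

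The adjusted analysis is not free either. In three null simulations of 4,000 trials, its one-sided error was 2.9–3.1%, against 2.5–2.6% unadjusted, with a simulation SE of about 0.25 points (√(0.025×0.975/4000)). That is a small excess.

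A reader might also infer more than the documents support:
- *That precision is definitely lost.* This needs prior cryotherapy to predict response. Section 1.3 reports one pooled response for cryotherapy "in a mixed group of primary therapy and rescue therapy for refractory disease", with no split, and rescue there does not mean failed cryotherapy. The refractory cohort in the same section had similar response across types of therapy.
- *That control has no untried ablation to offer such subjects.* Section 5.5.3 allows RFA and more than one cryotherapy device, and 1.3 describes both spray and balloon delivery.
- *That a 30-point advantage could come mostly from previously treated subjects.* Even assuming 20–30% prevalence and a 40–50 point difference in them, they contribute 0.20×40 = 8 to 0.30×50 = 15 of the 30 points, at most half. This would also be effect modification, which a main-effect term does not address.

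**Conclusion.** The omission is real but minor. Subjects with prior cryotherapy can enter, 5.1.1 most naturally asks for that history, control may be cryotherapy, and the variable is in neither 7.4 nor 7.5. The planned test remains valid and the stated power stands.

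The benefit of adding it depends on an effect that the documents do not quantify. Under the assumed gaps of 20 to 40 points, the gain over the planned model is roughly 1–8% of variance, and the term removes a shift of about 1–3 points per 10-point imbalance. With no effect, about 1% of variance is lost. The descriptive breakdown serves interpretation separately, and is more credible if fixed before results are seen.

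**What to change.** 1. In 5.1.1, define the item as prior cryotherapy, yes or no, and carry it into 5.1.2 and the baseline case report form.
2. Add it to the covariates in 7.4 and to both predictor lists in 7.5, so that the imputation models contain every covariate in the analysis model. State in advance that the term is dropped if fewer than 5 subjects fall in either category.
3. Pre-specify a descriptive table of the arm difference in subjects with and without prior cryotherapy, without a test.

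If the sponsor prefers to leave the primary model alone, a pre-specified sensitivity analysis with the added term, together with the table, meets most of the need.

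The cost is one defined data item, one binary model term and one table. The gain is small if prior cryotherapy proves rare or unrelated to response.

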5.5.2 Screen Failures

Enrolled subjects failing to meet inclusion / exclusion criteria at the time of index procedure will not be treated with the EndoRotor® device or the control device and; therefore, are classified as screen failures. Any baseline study data captured in the CRFs will be collected. Only subjects in whom the EndoRotor® catheter or ablative therapy catheter enters the esophagus will be followed and study data analyzed [per protocol set (PPS)].

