7.2 Analysis Populations

The safety analysis population is defined as all subjects who are treated with either EndoRotor® or continued ablative therapy. Subjects will be analyzed as treated.

The primary effectiveness analysis population is intent to treat (ITT), defined as all subjects who are randomized. Subjects will be analyzed as randomized. Missing primary and secondary endpoint data will be imputed.

A supportive effectiveness analysis population is Per Protocol (PP). This population is a subset of ITT and requires that subjects be treated with either EndoRotor® or continued ablative therapy, meet all inclusion/exclusion criteria, and are evaluated for effectiveness at no fewer than two post-treatment visits 3 months apart. Subjects will be analyzed as treated. Missing data will not be imputed.

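### The Protocol Summary makes per protocol the primary analysis, Section 7.2 makes ITT primary, and PP membership differs between sections

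*Combined protocol and SAP*

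**What the plan says.** **Primary population.** The Protocol Summary, Primary Analysis row: "Per protocol (subjects enrolled in the study and who met all I/E criteria and are treated with the device". Section 7.2: "The primary effectiveness analysis population is intent to treat (ITT), defined as all subjects who are randomized". The same section calls PP supportive.

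**Methods.** Section 7.4 is written for ITT: "In the event that missing data are present in the ITT analysis population, then multiple imputation will be performed". Section 7.5 supplies ten imputations, a seed, a predictor list, best-case and worst-case analyses, and a tipping-point analysis if those two disagree.

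**PP membership.** Like the Protocol Summary, Section 7.2 requires subjects to be eligible and treated, but it adds that they be "evaluated for effectiveness at no fewer than two post-treatment visits 3 months apart". Section 4.14 leaves it open whether a treated subject later found ineligible is removed from PP. It takes out subjects who withdraw before treatment and/or before the 9-month visit, and keeps in those whose procedure the investigator stops. Section 5.5.2 attaches the PP label to catheter entry alone: only subjects in whom the EndoRotor or "ablative therapy catheter enters the esophagus will be followed and study data analyzed [per protocol set (PPS".

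**Timing.** Section 5.5.3: "Randomization will occur within 2 weeks of the procedure". Section 5.5.2 has eligibility applied again at the index procedure. Subjects who fail there are not treated and are classed as screen failures.

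**Enrolment.** Section 4.9 dates enrolment from catheter insertion. Section 5.5.3 randomizes subjects who are already enrolled.

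**The concern.** A pivotal trial should have one primary population, fixed before outcomes are known. Here two sections name different ones, and a reader who starts from the Protocol Summary could present PP as the planned primary analysis.

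The Protocol Summary's set is conditioned on events after allocation: passing the eligibility check at the procedure, and being treated. The arms are resection and ablation, and for control "The investigator will choose the system in this arm", so whoever makes those decisions knows the assignment. Randomization no longer guarantees that the subjects left in each arm are comparable.

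The supportive analysis is unsettled too. The same subject can be inside PP under one section and outside it under another. Because enrolment has two meanings, the planned 120 enrolled cannot be matched with certainty to the ITT count.

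**Working it through.** **1. The plan's own figures.** Inputs from Section 7.3: 80% versus 50%, 55 evaluable per arm, margin 10 points. Section 7.1 gives two-sided 0.05.

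- Superiority, pooled-variance normal approximation, mean rate 0.65: z = [0.30 − 1.96·√(2·0.65·0.35/55)] / √((0.16 + 0.25)/55) = (0.30 − 0.1783)/0.0863 = 1.41, so power is 92.1% (stated: 91.6%).
- Non-inferiority: z = 0.40/0.0863 − 1.96 = 2.67, so power is 99.6% (stated: over 95%).
- 110 evaluable plus 10 lost = 120.

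The sample size is not in error. The conflict concerns who is analysed.

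**2. Who is in each set.**

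| Subject | Summary PP | 4.14 | 5.5.2 | 7.2 PP | 7.2 ITT |
|---|---|---|---|---|---|
| Randomized, ineligible at procedure, untreated | out | not addressed | out, not followed | out | in, outcome imputed |
| Treated, later found ineligible | out | discretionary | in | out | in |
| Eligible, treated, fewer than two post-treatment visits | in | out if withdrawn | in | out | in, imputed if outcome missing |

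No row is treated alike in every column. The second and third rows show that the PP texts also disagree among themselves.

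**3. Size of the disagreement.** The documents give no rate of exclusion after randomization. Assume 60 randomized per arm, with 2 per arm (2/2) or 5 per arm (5/5) lacking an outcome. Two uneven splits of ten were added: 7 EndoRotor/3 control and 3/7. The 5/5 case uses up the whole allowance of 10 for loss to follow-up. Exclusion is taken as unrelated to outcome.

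Section 7.5 lists its predictors ("The following variables will be used as predictors: site", then age, dysplasia grade, lesion length and disease duration). Treatment arm is not among them, so missing outcomes are drawn at roughly one common rate in both arms. The expected ITT difference then shrinks by the observed fraction:

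- 2/2: 30 × 58/60 = 29.0 points
- 5/5: 30 × 55/60 = 27.5 points; a true 20 points becomes 20 × 55/60 = 18.3

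Simulation used 200,000 trials per scenario. PP is a Wald 95% interval on subjects with an outcome. ITT is 60 per arm, ten imputations, Rubin's rules. Superiority means a lower bound above 0.

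| Missing (EndoRotor/control) | 80% vs 50%: PP power, ITT power, disagree | 70% vs 50%: PP power, ITT power, disagree |
|---|---|---|
| 2/2 | 94.1, 93.0, 1.2% | 60.7, 58.9, 2.3% |
| 5/5 | 93.1, 89.8, 3.2% | 59.9, 52.1, 8.0% |
| 7/3 | 92.6, 89.5, 3.1% | 59.4, 51.8, 7.7% |
| 3/7 | 92.2, 89.9, 2.3% | 57.6, 52.2, 5.6% |

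The non-inferiority decision differs in under 0.3% of trials at 80% versus 50%, and in 0.7 to 2.9% at 70% versus 50%.

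**4. Source of the tilt.** At 70% versus 50% with 5/5 missing, 7.9% of trials succeed on PP only and 0.1% on ITT only. With arm added to the imputation model, total disagreement falls to about 1% (80/50) and 2 to 4% (70/50). At 70/50 the split becomes 2.3% PP-only against 1.3% ITT-only for 5/5, and it reverses to about 0.8% against 2.1% for 3/7.

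**5. One trial.** Control 28/55, EndoRotor 38/55: difference 18.2 points, SE 9.18, lower bound 18.18 − 1.96 × 9.18 = +0.2, so PP passes. With 5/5 imputed at the common rate (66/110 = 60%, three successes per arm on average), the difference is 41/60 − 31/60 = 16.7 points and the mean lower bound is −1.4, so ITT usually fails. At 37/55 PP already fails (−1.8). At 40/55 both pass (ITT mean lower bound +2.2). The band in which the choice decides the result is narrow.

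**Limits.** Covariates and site are ignored, and binary draws stand in for the MCMC procedure. The simulated PP set drops everyone without an outcome. That fits Section 7.2, but it fits the Protocol Summary's set only if all the exclusions occur before treatment.

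**The case against.** The strongest reply is that the intended plan can be recovered. Sections 7.2, 7.4 and 7.5 all work on ITT, and the seed, predictor list and sensitivity analyses would have little purpose under a PP primary. On that view the Protocol Summary holds one row that was never aligned. This largely stands, and it is why ITT is the side to keep. It does not remove the need for correction, since no clause gives Section 7 precedence and Section 5.5.2, in the body, also points to a PP analysis.

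Four stronger readings are tempting and not supported:

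- *PP has four rival definitions.* Only the Protocol Summary and Section 7.2 are worded as definitions, and the second is the first plus a visit requirement. Section 4.14 is a list of disposition rules whose withdrawal sentence is cut off in the text available. Section 5.5.2 is a screen-failure rule carrying a PP tag. The inconsistencies in membership are nevertheless real.
- *PP inherently favours the device.* The one-way pattern comes from leaving arm out of the imputation predictors, which is a separate defect.
- *Randomized, untreated subjects are lost from the primary analysis.* Read literally, Section 5.5.2 would do this. But Section 7.2 keeps them in ITT, and Section 7.5 already imputes their outcomes and tests sensitivity. One clarifying clause is missing.
- *The effect is large.* Bigger gaps appear if untreated subjects are scored as failures, but the plan contains no such rule.

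**Conclusion.** The contradiction over the primary population is in the current text and should be corrected before outcome data are seen. ITT is the better-supported reading, and the Protocol Summary row is the outlier. The PP wording in Sections 4.14 and 5.5.2 does not agree with Section 7.2.

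The measurable consequence is modest: the disagreement on superiority is about 1 to 3% of trials at the design rates and about 2 to 8% at 70% versus 50%. This rests on the assumed 60 per arm, on 4 to 10 subjects in all without an outcome, and on exclusion unrelated to outcome. The case for correction therefore rests mainly on two things that these figures do not capture: the freedom to choose a population once results are known, and the possibility of selective exclusion by an investigator who knows the arm. The latter is plausible, but the documents give nothing from which to size it.

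**What to change.** 1. Change the Primary Analysis row of the Protocol Summary to ITT as defined in Section 7.2. Keep PP supportive, and report it alongside ITT for the non-inferiority test.
2. Use the single Section 7.2 definition of PP in the Protocol Summary, Section 4.14 and Section 5.5.2, with individual exclusions fixed before outcome data are seen.
3. State in Section 5.5.2 that its restriction defines the PP set only. Randomized, untreated subjects stay in ITT and are handled by the imputation and sensitivity analyses already in Section 7.5.
4. Reconcile the meaning of enrolment in Sections 4.9 and 5.5.3, so that the 120 can be matched to the ITT set.

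The cost is wording only, with no added visits or subjects. The ITT estimate may be slightly less favourable than PP: about 27.5 against 30 points at the design rates with ten missing outcomes and the Section 7.5 predictors as listed.
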